9.8. Sample Collection and Handling

Beginning with the implementation of Amendment 7, samples will no longer be collected in this study.

The actual dates and times of sample collection must be recorded in the CRF or laboratory requisition form. Refer to the Time and Events Schedule for the timing and frequency of all sample collections.

Instructions for the collection, handling, storage, and shipment of samples are found in the Laboratory Manual. Collection, handling, storage, and shipment of samples must be under the specified, and where applicable, controlled temperature conditions as indicated in the Laboratory Manual.

10. SUBJECT COMPLETION/DISCONTINUATION OF STUDY TREATMENT/ WITHDRAWAL FROM THE STUDY

10.1. Completion

A subject will be considered to have completed study treatment if he or she has completed all planned administrations of the study drug(s) in the assigned treatment arm. A subject will be considered to have completed the study if he or she has finished all protocol-specified procedures before the end of the study, has died before the end of the study, has not been lost to follow up, and has not withdrawn consent for study participation before the end of the study.

10.2. Discontinuation of Study Treatment/Withdrawal from the Study

Discontinuation of Study Treatment

A subject will not be automatically withdrawn from the study if he or she has to discontinue treatment. The End-of-Treatment Visit and Follow-up visit assessments should continue as specified in the Time and Events Schedules.

A subject's study treatment must be discontinued if:

- The investigator believes that for safety reasons or tolerability reasons (eg, adverse event) it is in the best interest of the subject to discontinue study treatment
- The subject becomes pregnant
- The subject (or the subject's legally acceptable representative) withdraws consent for administration of study treatment
- The subject experiences unacceptable toxicity, including IRRs described in Section 6.3
- The subject missed more than 2 consecutive planned doses due to daratumumab-related AEs
- The subject missed more than 105 consecutive treatment days due to atezolizumab-related AEs
- The subject experiences confirmed disease progression (per RECIST 1.1), see Table 12.
- A subject who experiences a second primary malignancy that cannot be treated by surgery alone must be withdrawn from the study. However, a subject who develops a malignancy that can be cured surgically may continue to receive the assigned study treatment and should continue to be followed for subsequent progression of NSCLC.

The primary reason for discontinuation of study treatment is to be recorded in the CRF.

Withdrawal From the Study

A subject will be withdrawn from the study for any of the following reasons:

- Lost to follow-up
- Withdrawal of consent to study participation
- Pregnancy
- Second primary malignancy (see Discontinuation of Study Treatment for additional details)
- Death
- The study investigator, for any reason, stops the subject's participation in the study
- Sponsor terminated the study

Before a subject is lost to follow-up, every reasonable effort must be made by the study-site personnel to contact the subject and determine the reason for discontinuation/withdrawal. The measures taken to follow up must be documented.

When a subject withdraws before completing the study, the reason for withdrawal is to be documented in the CRF and in the source document. Study drug assigned to the withdrawn subject may not be assigned to another subject. Subjects who withdraw will not be replaced. If a subject discontinues from treatment, end-of-treatment assessments should be obtained.

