4.1. Inclusion Criteria

Investigators should ensure that all study enrollment criteria have been met at Screening. If a subject's clinical status changes (including any available laboratory results or receipt of additional medical records) after screening but before the first dose of study drug is given such that he or she no longer meets all eligibility criteria, then the subject should be excluded from participation in the study. Section 9.1.3, Screening Phase, describes options for retesting. Section 17.4, Source Documentation, describes the required documentation to support meeting the enrollment criteria.

Each potential subject must satisfy all of the following criteria to be enrolled in the study:

1. ≥ 18 years of age
2. ECOG performance status of 0 or 1.
3. Criterion modified per Amendment 2.
 - 3.1 Criterion modified per Amendment 3.
 - 3.2 Have histologically or cytologically confirmed advanced or metastatic NSCLC (Stage IIIb or greater).
 - Subjects must have received at least 2 cycles of standard platinum-based therapy for Stage IIIb or greater NSCLC and had disease progression on or after therapy.

Note: Subjects who have received fewer than 2 cycles of platinum-based therapy due to intolerance (history of hypersensitivity or allergic reactions and other adverse events which prevent continuation of platinum-based agent), are eligible for study participation, provided there is documentation of disease progression.

 - Subjects who received prior treatment with vaccines or investigational agents, are eligible for study participation.
 - Subjects with known genetic alterations of *ALK*, *EGFR*, and *ROS1* are not eligible for study participation.
4. Criterion modified per Amendment 2.
 - 4.1 Measurable disease, as defined by RECIST 1.1.
5.
 - 5.1 Criterion modified per Amendment 4.
 - 5.2 Criterion modified per Amendment 5
 - 5.3 Criterion modified per Amendment 6

Tumor cell PD-L1 score as determined by an IHC assay performed by the central laboratory on tissue obtained after the last line of therapy:

Randomized phase of the study

 - Subjects with a tumor cell PD-L1 score of TC1-3 who are anti-PD-1 or anti-PD-L1 treatment naïve will be eligible for screening.
6. Criterion modified per Amendment 2.
 - 6.1 Criterion modified per Amendment 3.

6.2 Laboratory values that meet the following criteria within 14 days prior to first administration of study drug (see Table 1):

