9.1.4. Open-Label Treatment Phase

Details of the procedures performed during the Treatment Phase are outlined in the Time and Events Schedule (Table 1). Subjects in the randomized phase should start study treatment within 72 hours after randomization. A window of ± 1 day for Cycles 1 to 3 for subjects receiving daratumumab and ± 3 days for all other drug administration visits is allowed for drug

administration visits to the clinic. Clinical evaluations and laboratory studies may be repeated more frequently than outlined in the Time and Events Schedule, if clinically indicated. If treatment is discontinued, the subject will complete the End-of-Treatment assessment, and enter the Follow-up Phase.

End of Treatment

Unless a subject withdraws consent for study participation or is lost to follow up, an End-of-Treatment Visit is to occur at 30 days after the last dose of study treatment. A delay of this visit to up to 7 days is permitted. Every effort should be made to conduct the End-of-Treatment Visit before the subject starts subsequent treatment. If a subject is unable to return to the site for the End-of-Treatment Visit, then the subject should be contacted to collect information on Grade 2 or higher adverse events and concomitant medications used to treat Grade 2 or higher adverse events, any immune-related AE, or any infusion-related reactions until disease progression. Additional information on reporting of AEs is presented in Section 12.

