9.1.5. Follow-Up Phase

The posttreatment Follow-up Phase will begin once the subject completes the End-of-Treatment evaluation. Reasons for discontinuation of study treatment are listed in Section 10.2. Subjects who discontinue treatment before disease progression must continue to have disease evaluations as described in Table 1 and Section 9.4 (every 6 weeks [± 1 week] for the first 12 months of after the start of treatment and every 9 weeks [± 1 week] thereafter regardless of treatment delays). After disease progression is confirmed, follow-up for survival status and subsequent anti-cancer therapy will be obtained at least every 12 weeks after the last dose of study drug, until the subject has died, is lost to follow-up, or has withdrawn consent. If the information on survival status is obtained via telephone contact, written documentation of the communication must be available for review in the source documents. If the subject has died, the date and cause of death will be collected and documented on the CRF.

The end of the study is anticipated to be 24 months after the last subject has been enrolled (last patient in) or when the last subject has the last assessment in this study (eg, last survival follow-up for the last subject), whichever occurs first.

Investigators may recontact the subject to obtain long-term follow-up information regarding the subject's safety or survival status as noted in the informed consent form (refer to Section 16.2.3, Informed Consent).

Subjects will be instructed that study drug will not be made available to them after they have completed/discontinued study drug and that they should return to their primary physician to determine standard of care.

Beginning with the implementation of Amendment 7, data from safety evaluations performed according to local regulatory approvals and standard of care guidelines^{50,51} will no longer be collected with the exception of serious adverse events that are to be reported and entered in the Sponsor safety repository.

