11.2. Sample Size Determination

Assuming that the ORR for atezolizumab monotherapy is approximately 20%, and the addition of daratumumab would improve ORR by 20% to 40%, 90 subjects need to be randomized with a 1:1 ratio in order to achieve 80% power to detect this difference with a one-sided alpha of 0.10. In the event that benefit from the combination is not observed across the overall study population, targeted enrollment of subgroups, based on tumor PD-L1 expression level, may be implemented, based on DMC recommendations (see Section 11.3). As such, approximately 50 additional subjects in the TC2/TC3 subgroups may be enrolled to preliminarily evaluate the treatment effect. If the ORR is 25% for atezolizumab monotherapy and 50% for the atezolizumab + daratumumab combination in the TC2/TC3 subgroup, the lower bound of the 90% CI for the difference in ORR would exclude 0 (ie, a positive signal in favor of the combination).

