12.6. Pregnancy

All initial reports of pregnancy in female subjects or partners of male subjects must be reported to the Sponsor by the study-site personnel within 24 hours of their knowledge of the event using the appropriate pregnancy notification form. Abnormal pregnancy outcomes (eg, spontaneous abortion, fetal death, stillbirth, congenital anomalies, ectopic pregnancy) are considered serious adverse events and must be reported using the Serious Adverse Event Form. Any subject who becomes pregnant during the study must be promptly withdrawn from the study and discontinue further study treatment.

Because the effect of the study drug on sperm is unknown, pregnancies in partners of male subjects included in the study will be reported as noted above.

Follow-up information regarding the outcome of the pregnancy and any postnatal sequelae in the infant will be required.

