5.3.4. Overall Survival

Definition

Overall survival (OS) is defined as time from date of randomization to date of subject's death from any cause. For subjects who are still alive at the end of study or lost to follow-up, OS will be censored on the date the subjects were last known to be alive. Overall survival is calculated in months as follows:

$$\text{OS} = (\text{date of death or censoring} - \text{date of randomization} + 1) / (365.25/12).$$

Analysis Methods

The number and percentage of subjects who were died or still alive will be reported. The Kaplan-Meier method will be used to estimate the distribution of OS for each treatment group, and the median OS with 95% CI will be provided. In addition, the Kaplan-Meier PFS curve will also be presented by treatment group.

Hazard ratio (Arm B vs. Arm A) and its 95% confidence interval will be presented. In addition, 3, 6, 12-months of OS rate with 95% CI will be estimated by Kaplan-Meier method and reported for each treatment group.

OS will also be presented by the subgroups specified in Section 2.4, as appropriate.

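### Protocol Sections 10.2 and 12.6 withdraw subjects from the study, not only from treatment, for reasons that Section 9.1.5 does not accept as ending survival follow-up

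*Protocol*

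**What the plan says.** Protocol Section 10.2 opens with a sound principle: stopping study treatment does not by itself remove a subject from the study. Three of its rules then go further.

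- **Second malignancy.** Inside the list of reasons for stopping treatment, the protocol states: "A subject who experiences a second primary malignancy that cannot be treated by surgery alone must be withdrawn from the study". A subject whose new cancer is surgically curable may stay on treatment and goes on being followed for progression. Second primary malignancy appears again in the separate list of study-withdrawal reasons.
- **Pregnancy.** It is in the study-withdrawal list, and Section 12.6 repeats it: "Any subject who becomes pregnant during the study must be promptly withdrawn from the study".
- **Investigator decision.** The study-withdrawal list includes: "The study investigator, for any reason, stops the subject's participation in the study".

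Section 9.1.5 asks for survival status at least every 12 weeks after confirmed progression, "until the subject has died, is lost to follow-up, or has withdrawn consent". None of the three reasons above is among those end points.

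SAP Section 2.3.1 keeps everyone who entered the randomization phase in the ITT set. SAP Section 5.3.4 reads: "Overall survival (OS) is defined as time from date of randomization to date of subject's death from any cause". Its censoring sentence covers subjects alive at the end of the study or lost to follow-up, and does not mention subjects withdrawn by rule. SAP Section 5.3.3 censors PFS at the last tumor assessment when a subject drops out.

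**The concern.** OS and PFS are compared between randomized arms, so follow-up should end for reasons unrelated to outcome. Two of the three exits may not meet that test. A new cancer that surgery alone cannot treat is plausibly linked to prognosis. An investigator's decision, in an open-label trial, is made by someone who knows the arm. If such subjects are censored when they leave, the censoring may be informative, and it would come from a protocol rule and not from the subject's wish. Pregnancy is not obviously prognostic and will be rare in this population; it belongs here because it creates the same conflict of wording.

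Survival data carry weight in this trial. Protocol Section 1.4 records that the DMC noted numerically more deaths in the combination arm at its third review (44 subjects per arm). Complete survival status makes that observation easier to read.

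**Working it through.** **1. Do the sections conflict?**

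| Reason for leaving | Section 10.2 / 12.6 | End of survival follow-up in 9.1.5? |
|---|---|---|
| Death, loss to follow-up, withdrawn consent | leaves the study | yes |
| Second malignancy not treatable by surgery alone | leaves the study | no |
| Pregnancy | leaves the study | no |
| Investigator decision, any reason | leaves the study | no |

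They do. Section 3.1 sharpens the second-malignancy row. It schedules survival contact every 12 weeks after progression or the start of new anticancer therapy. A subject who begins systemic therapy for a second cancer would qualify for that contact, while Section 10.2 removes the same subject.

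**2. Does a Section 10.2 exit end data collection?** No sentence says that survival contact stops. Two neighbouring rules point that way. Section 3.1 ends disease assessments when a Section 10.2 withdrawal criterion is met. Section 12.4 collects late related serious adverse events only until the subject leaves the study as defined in Section 10.2. Section 9.1.5 lets investigators recontact subjects for survival status but does not require it. Loss of survival status is therefore a reasonable inference, not a stated rule.

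**3. What would be lost on the primary endpoint?** First, the plan's own sample size. Inputs from Protocol Section 11.2: ORR 20% versus 40%, 1:1 allocation, one-sided alpha 0.10, power 80%, 90 subjects.

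- Unpooled formula: n per arm = (1.2816 + 0.8416)² × (0.20×0.80 + 0.40×0.60) / 0.20² = 45.08, or 90.2 in total. The plan's 90 reproduces.
- Power at 45 per arm: 79.0% (pooled variance), 79.9% (unpooled), 80.0% (exact, likelihood ratio test).

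No allowance for withdrawal is stated, and Section 10.2 does not replace subjects who withdraw. The documents give no withdrawal rate, so a share d of 2%, 5% or 10% lost before a response is assessed is **assumed**. Pooled power is recomputed with response rates multiplied by (1 − d) if lost subjects count as non-responders, or with n multiplied by (1 − d) if they are excluded.

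| Assumed d | Subjects of 90 | Power, non-responders | Power, excluded |
|---|---|---|---|
| 0 | 0 | 79.0% | 79.0% |
| 2% | 1.8 | 78.2% | 78.4% |
| 5% | 4.5 | 76.8% | 77.5% |
| 10% | 9 | 74.4% | 75.8% |

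**4. What would be lost on OS?** If the same share of events is lost, the standard error of the log hazard ratio grows by 1/√(1 − d) − 1: 1.0%, 2.6% and 5.4%. This measures precision only. Bias from informative censoring depends on which subjects leave which arm, and nothing in the documents allows it to be calculated.

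**The case against.** The best defence is that survival status can still reach the analysis. Section 9.1.5 sets its own end points and permits recontact. The consent described in Section 16.2.3 covers survival information. SAP Sections 2.6.8 and 5.3.4 work from the date last known alive, not the withdrawal date. Section 12.3.1 keeps serious adverse event reporting open for 90 days after the last dose, cut short only by new anticancer therapy or withdrawn consent, so many early deaths in dosed subjects would be seen. All of this stands. It means a reader should not infer that deaths go uncounted by rule. It does not remove the point, because none of these routes requires continued contact after a Section 10.2 exit.

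A reader might also infer that Section 4.1 removes randomized subjects. It says that if status changes before the first dose "then the subject should be excluded from participation in the study", and Section 9.1.4 says "Subjects in the randomized phase should start study treatment within 72 hours after randomization", which leaves a gap after allocation. The documents do not support building on this. Section 4.1 is general enrollment text, makes no mention of randomized subjects, and sits beside a SAP that keeps them in ITT. Nor does follow-up necessarily fail to start for an undosed subject: Section 9.1.5 counts from the last dose, but Section 3.1 and SAP Section 1.2 tie survival contact to progression or new therapy. What stands is narrower: no text says from which date survival contact runs for someone randomized but never dosed.

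Finally, the practical reach is small. Enrollment closed on 25 May 2018, Amendment 7 describes the database as locked, and OS is a secondary endpoint reported as a hazard ratio with its interval. That is correct, and it limits what can now be gained.

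**Conclusion.** The conflict is real and comes from the text itself. Sections 10.2 and 12.6 withdraw subjects from the study for three reasons that Section 9.1.5 does not treat as ending survival follow-up. Followed as written, Section 10.2 may censor ITT survival data early and possibly informatively.

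The size is unknown and probably small. It would be tempting to assign a rate to each exit, multiply by a mortality figure and report a number of hidden deaths. The documents contain neither the rates nor any record of such a withdrawal, so that number would only restate the assumptions. The direction of any bias between arms is not shown either.

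The effect on ORR is minor. One subject is 1/45 = 2.2 percentage points of an arm, but only if that subject would have responded. At the planned ORR of 20% to 40% the expected effect is 0.2 × 2.2 = 0.4 to 0.4 × 2.2 = 0.9 points. The power figures above say the same.

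The conclusion rests on reading withdrawal from the study as ending mandatory contact, which Sections 3.1 and 12.4 support but no sentence states.

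**What to change.** - **Protocol 10.2 and 12.6.** Reconcile with 9.1.5. Second primary malignancy, pregnancy and investigator decision should end study treatment only, and survival status should still be collected every 12 weeks, by telephone if needed, unless the subject withdraws consent to follow-up. Whether and when treatment is stopped or not started is outside this point.
- **SAP 5.3.4.** State that subjects who leave for these reasons are censored for OS at the date last known alive, not at withdrawal. PFS gains less: SAP 5.3.3 would still censor at the last tumor assessment if scans stop.
- **Randomized but not dosed.** Say that survival status is obtained, counted from randomization. No added imaging is needed.
- **Still possible now.** In the clinical study report, give by arm the number withdrawn for each of these reasons and whether survival status is known. Section 10.2 already has the reason recorded in the CRF, and SAP Section 4.2 already tabulates it; the survival-status column is the only addition.

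The cost is some wording and a few extra survival contacts. Section 9.1.5 already allows telephone contact, and the consent in Section 16.2.3 covers survival status.

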10.3. Withdrawal From the Use of Research Samples

A subject who withdraws from the study will have the following options regarding the optional research samples:

- The collected samples will be retained and used in accordance with the subject's original informed consent for optional research samples.
- The subject may withdraw consent for optional research samples, in which case the samples will be destroyed and no further testing will take place. To initiate the sample destruction process, the investigator must notify the Sponsor study site contact of withdrawal of consent for the optional research samples and to request sample destruction. The Sponsor study site contact will, in turn, contact the biomarker representative to execute sample destruction. If requested, the investigator will receive written confirmation from the Sponsor that the samples have been destroyed.

Withdrawal From the Optional Research Samples While Remaining in the Main Study

The subject may withdraw consent for optional research samples while remaining in the study. In such a case, the optional research samples will be destroyed. The sample destruction process will proceed as described above.

Withdrawal From the Use of Samples in Future Research

The subject may withdraw consent for use of samples for research (refer to Section 16.2.5, Long-Term Retention of Samples for Additional Future Research). In such a case, samples will be destroyed after they are no longer needed for the clinical study. Details of the sample retention for research are presented in the main ICF and in the separate ICF for optional research samples.

11. STATISTICAL METHODS

Statistical analysis will be done by the Sponsor or under the authority of the Sponsor. A general description of the statistical methods to be used to analyze the efficacy and safety data is outlined below. Specific details will be provided in the Statistical Analysis Plan.

